10. STATISTICAL PROCEDURES

10.1 ANALYSIS POPULATIONS

All primary analyses will be conducted on an intention to treat (ITT) basis with imputation for missing data as described in the Patient Accountability and Missing Data section below. Whereas ITT is a concept intended to be applied to randomized trials, its use in this analysis will imply that patients will be analyzed based on the attempt to implant trial devices during the procedure. Patients who complete the trial through 12 months will comprise the completed cases (CC) population. CC patients who do not have protocol violations that can affect outcome will comprise the per protocol (PP) population. Additional analyses will be conducted in the CC population.

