10.2 PATIENT ACCOUNTABILITY AND MISSING DATA

The proportion of patients with documented follow-up at each interval will be presented descriptively. The number of diagnostic, laboratory, and clinical evaluations will be tabulated by follow-up interval. Also, a listing of patients who initially consent but do not undergo a procedure due to withdrawal of consent will be given. However, these patients will not be included in any analysis.

Information on missing or withdrawn patients will be tabulated presenting the number and proportion of patients eligible for and compliant with each follow-up examination. Patients who withdraw from the trial will be tabulated with the reasons for the withdrawal. Additional sensitivity analyses will be performed as described below.

The evaluation of patients with missing data presents a special concern in ITT analyses. All clinical studies analyze the results based on the completed cases (i.e., those who complete the trial). Because missing patients do not have final data, they present a problem for ITT analyses. The statistical community recommends that multiple sensitivity analyses be conducted to determine the robustness of the result in patients who complete the study.^{10,11,12,13} The intention of these analyses is to demonstrate that the results obtained from the evaluable patients are not biased.

As a result, sensitivity analyses using multiple imputations will be conducted to evaluate the robustness of the study result accounting for missing observations. The primary effectiveness endpoint analysis will be based on an unbiased imputation of the determination of success or failure. It is expected that the number of patients with missing effectiveness data at one year will be approximately 15 patients (i.e., 15%). The missing value for these patients will be assigned by a simple random sample from the patients with outcomes at one year. This system is denoted the “Hot

¹⁰Pocock S. (1983). *Clinical Trials (A Practical Approach)*. John Wiley and Sons, Chichester.

¹¹Friedman L, Furberg C, and DeMets D. *Fundamentals of Clinical Trials*. 1985: Mosby Year Book, St. Louis.

¹²Guidance for Industry: E9 Statistical Principles for Clinical Trials. U. S. Department of Health and Human Services, Food and Drug Administration, Center for Drug Evaluation and Research and Center for Biologics Evaluation and Research. International Committee on Harmonization, September 1998.

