¹³Rubin D. *Multiple Imputation for Nonresponse in Surveys*. 1987: John Wiley and Sons, New York.

Deck by Simple Random Sampling with Replacement".¹⁴ The number of patients to impute is small and trying to provide a more sophisticated imputation method would require modeling missingness with only approximately 15 patients or less with missing data. Additional sensitivity analyses will be done by using other imputation methods. The first shall be the last observation carried forward (LOCF). Another sensitivity analysis will entail considering the subject lost to follow-up to have failed the endpoint. A third analysis will impute the missing result as having succeeded the endpoint. A final analysis will impute the missing value by a generating a random number and comparing it to the value of the performance goal for effectiveness.

A comparison of baseline characteristics of the patients with missing data and those without missing data will be done to determine if there is evidence that the data are not missing at random (it is not possible to determine that data are missing at random). If the missing at random assumption is clearly violated by these comparisons, it is usually possible to find a sub-group that are not missing at random who have to be imputed differently, such as assigning the worst score to patients in the sub-group. For example, the proportion of patients missing an outcome may be much greater at a given study site which may also have a higher rate of failure. Those patients from that site may be assigned a failure and the baseline comparisons of the remaining patients will be rechecked to see if the imbalances are resolved. If this resolves the missing at random difficulty, the sub groups will be given special scores and the remaining patients will be imputed as described above. The resolution of the imbalance will be retested by the same methods with the patients identified above removed.

The primary imputation will be done 10 times with 10 different seeds to initiate the random selection and the combined P-value for the 10 imputations will be obtained by a method described in Rubin (1987) and in the SAS manual for PROC MIANALYZE. The seeds to be used for the 10 imputations are selected from a pseudo-random number table in Steele and Torrie (1960) and are 70303, 18191, 62404, 26558, 92804, 15415, 02865, 52449, 78509, and 43896.¹⁵

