10.3 GENERAL NOTES

Analyses of MAEs and other adverse events will be conducted at exact time points. Early events are defined as those occurring from the date of the procedure to 30 calendar days post-operatively. Late events are defined as those occurring from after 30 calendar days post-operatively (from day 31 forward). Events within six months and one year, respectively, are those occurring up to and including 183 days and 365 days following the procedure.

For categorical variables, summary statistics will include counts and proportions. Confidence limits for proportions will generally be given; for binary variables the confidence limits will be computed

¹⁴Little R and Rubin D. *Statistical Analysis with Missing Data*. 2002. John Wiley and Sons, New York.

¹⁵Steele R and Torrie J. *Principles and Procedures of Statistics*. 1960. McGraw-Hill, New York.

using the exact binomial distribution. Supportive multivariate analyses of stratified comparisons of categorical variables will be performed using appropriate logistic or Cox regression.

For continuous variables, summary statistics will include means, standard deviations, medians, and range. Groups will be compared using *t*-tests or analysis of variance, or Kruskal-Wallis tests will be used to compare more than two groups (such as trial sites). When multiple comparisons are performed after ANOVA, Scheffé's method will be used. The exact Wilcoxon test will be used to compare continuous variables where severe departures from normality are observed.

For ordinal variables, comparisons will be performed using the exact Wilcoxon rank-sum test. Unless otherwise specified, the exact form of each algorithm will be the default of SAS[®] Version 9.1 or later. Some preliminary descriptive analyses may be done with other software tools to be specified.

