10.7.3 Analysis Plan

The primary effectiveness analysis will compare the Treatment Success rate as defined previously to a target rate of 80%. The null and alternative hypotheses are defined below.

$$H_0: P_t \leq 0.80$$

$$H_1: P_t > 0.80$$

Where P_t = the proportion of treated patients who meet the Treatment Success definition. The observed proportion of patients with Treatment Success at one year post-procedure will be tested with the exact binomial distribution under the null hypothesis given in the inequality above. The formula for this expression is presented below.

$$P(X > x_t | 0.80) = \sum_{k=x_t}^{n_t} \binom{n_t}{k} 0.80^k 0.20^{n_t-k} < 0.05$$

Where x_t is the number of successes at one year and n_t is the number evaluated. If the one-sided P-value is less than 0.05, the null hypothesis will be rejected and the study hypothesis will be demonstrated.

If the study site success proportions across study site are not homogeneous, then the method of Fleiss described above will be used in the Test arm only to obtain a weighted estimate of the proportion successful. The mean proportion is found the same way as the first equation above. The test statistic becomes a z-statistic with the following formula:

$$z = \frac{(\bar{p}_T - 0.80)}{SE(\bar{p}_T)}$$

Where the formula for the weighted estimate of the proportion is given by the following formula.

$$\bar{p}_T = \frac{\sum_k W_k p_{Tk}}{\sum_k W_k}$$

And the formula for the weight in site k is given by the following

$$W_k = \frac{1}{n_k} p_k (1 - p_k)$$

And the formula for the standard error is given by the following.

$$SE(\bar{p}_T) = \left(\sum_{k=1}^{m_T} W_{Tk} \right)^{-1/2}$$

If the $z < 1.645$ ($P=0.05$, one-sided), then the null hypothesis will be rejected in favor of the alternative and the primary effectiveness endpoint will be achieved.

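### Primary effectiveness has two unreconciled decision rules, a Rubin-pooled hot-deck P-value and an exact binomial test, and the pooled rule names neither scale nor variance

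*Combined protocol and SAP*

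**What the plan says.** Section 10.1: "All primary analyses will be conducted on an intention to treat (ITT) basis with imputation for missing data as described" in Section 10.2. Section 10.2: "The primary effectiveness endpoint analysis will be based on an unbiased imputation of the determination of success or failure". About 15 patients are expected to lack a one-year outcome. Each missing value is drawn at random, with replacement, from patients who have one. This is done ten times with listed seeds, and "the combined P-value for the 10 imputations will be obtained by a method" attributed to Rubin (1987) "and in the SAS manual for PROC MIANALYZE". The same section also says that "sensitivity analyses using multiple imputations will be conducted to evaluate the robustness of the study result", which gives multiple imputation a second role.

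Section 10.7.3 says that the observed proportion is "tested with the exact binomial distribution under the null hypothesis". Its denominator is the number of patients evaluated, its rejection rule is one-sided P below 0.05, and it is silent on imputation. The synopsis (Section 3, Statistical Considerations) also names the exact binomial test, but gives no such denominator and defines ITT as all patients enrolled and treated. Section 10.7.2 sizes the trial with the exact test: 82 patients at one year, 80.58% power, raised to 97 for 15% drop-out.

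**The concern.** Two sections each state how the primary effectiveness null is rejected, and no section ranks them. Sections 10.1 and 10.2 lean towards the imputed P-value, yet 10.7.3 has a complete rule without it. The pooled rule is also not fully defined: Rubin's method needs a point estimate, a scale and a within-imputation variance, and none is given. The clause in Section 10.3 that "the exact form of each algorithm will be the default of SAS" does not help, because MIANALYZE pools whatever estimate and standard error it is given.

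At stake is the pass or fail of a primary endpoint near its threshold. The level of the deciding test would also depend on a choice that could be made after the data are seen.

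**Working it through.** **Inputs.** Goal 0.80, alternative 0.90, one-sided 0.05, 82 at one year, 15% drop-out (Section 10.7.2). About 15 missing and ten imputations (Section 10.2). Assumption: outcomes missing at random.

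**1. The plan's own figure.** Exact binomial, n = 82: P(X ≥ 71 | 0.80) = 0.0836 and P(X ≥ 72 | 0.80) = 0.0458, so 72 or more rejects. Power is P(X ≥ 72 | 0.90) = 0.8057, which agrees with the stated 80.58%. 82/0.85 = 96.5, rounded up to 97. The stated power therefore belongs to the exact rule on 82 evaluated patients.

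**2. Exact test on completed data.** If all 97 count as evaluated after imputation, each completed data set needs 85/97 (alpha 3.5%, power 83.0%). That leaves ten exact P-values and no rule to combine them.

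**3. The pooled rule.** With M = 10, Q the mean of the ten proportions, U the mean within-imputation variance and B the between-imputation variance:

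t = (Q − 0.80)/sqrt(U + 1.1 × B), df = 9 × (1 + U/(1.1 × B))²

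Candidates for U are p(1−p)/97 (usual) and 0.80 × 0.20/97 = 0.00165 (null). A third choice is to pool on the logit scale.

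**4. Worked case, 71 of 82.** p = 0.8659 and p(1−p) = 0.1162. A typical B is 15 × 0.1162/97² = 0.000185, so 1.1 × B = 0.000204.
- Usual: 0.0659/sqrt(0.001197 + 0.000204) = 1.76, P about 0.039, passes.
- Null: 0.0659/sqrt(0.001649 + 0.000204) = 1.53, P about 0.063, fails.
- Exact on 82: P = 0.084, fails.

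**5. Operating characteristics, 82 observed and 15 missing (simulated).**

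| | Exact on 82 | Usual | Null | Logit |
|---|---|---|---|---|
| Type I error at 0.80 | 4.6% | about 7.6% | 5.0% to 5.1% | about 4.5% |
| Power at 0.90 | 80.6% | about 87% | about 81% | about 80% |
| 71/82 passes | no | 76% of draws | 18% | 10% |
| 72/82 fails | no | 0.2% | about 7% | 16% |
| Disagrees with exact at 0.90 | – | about 6% | 2.2% | 2.6% |

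At 70/82 (exact P = 0.139) the usual-variance rule still passes in about 4% of draws. At 69 or fewer, or 73 or more, the rules agree apart from fractions of a percent.

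**6. Source of the excess.** With no missing data, the usual-variance z-test on 97 rejects at 84: p = 0.866, z = 0.066/sqrt(0.866 × 0.134/97) = 1.91 (at 83, z = 1.56). P(X ≥ 84 | 0.80) = 6.2%. Much of the rise to about 7.6% is therefore the normal approximation, not the imputation.

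**The case against.** The strongest reply is that there is only one rule. Section 10.1 puts every primary analysis on imputed ITT data, 10.2 speaks of the primary imputation, and 10.7.3 can be read as the test applied to the completed data. That is a fair reading of intent, and the synopsis does not contradict it, because the denominator of evaluated patients appears only in 10.7.3. It does not supply a usable test, though: ten exact P-values remain and the cited method does not pool them.

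A reader might infer that the plan commits to a test with a 7.6% error rate. The documents do not support that. The figure needs the usual variance, which the plan never names, and the null-variance and logit versions are close to nominal. Nor should one infer that analysts could redraw until they pass, since the seeds are fixed in advance. What is open is the choice of test. The reach is also narrow, a few counts around 72 of 82.

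The further imputations in 10.2 (last observation carried forward, all failures, all successes, draws at the performance goal) are sensitivity analyses and do not say which P-value decides. The clause on sub-groups "imputed differently, such as assigning the worst score to patients in the sub-group" is triggered by baseline imbalance and does not settle it either.

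One objection adds to the problem. Under site heterogeneity, Sections 10.5 and 10.7.3 replace the exact test with a site-weighted z-test, and 10.5 also calls for that method when P exceeds 0.15. This is a further deciding rule, with no link to the imputations.

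**Conclusion.** The concern holds as a conflict between decision rules together with an under-specified pooled test. It should be corrected. The level could lie anywhere from about 4.5% to about 7.6%, depending on an unstated choice. Opposite conclusions are essentially confined to 70 to 72 of 82, or about 2% to 6% of trials at true success 0.90. These sizes assume 15 of 97 missing at random and no site-heterogeneity branch. The plan's sample size arithmetic is correct for the exact rule and is not in question.

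**What to change.** **Preferred; keeps the ITT imputation of 10.1.** State in both 10.2 and 10.7.3 that the deciding test is

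z = (pooled proportion − 0.80)/sqrt(0.16/97 + 1.1 × B)

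with Rubin's degrees of freedom, B the between-imputation variance and 97 the ITT number. State that p(1−p)/n is not pooled. Then:
- replace the exact-binomial wording in the synopsis and 10.7.3;
- restate the power in 10.7.2: about 81%, 83% or 85% with 15, 10 or 5 missing;
- disclose that the level is about 5.0% to 5.1% with 15 missing, so marginally above nominal;
- report the exact test on evaluated patients as a sensitivity analysis;
- state that patients with a failure component already observed remain failures and are not imputed.

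**Alternative.** Make the exact test on evaluated patients primary and the hot deck a sensitivity analysis, and change 10.1 and 10.2 to match. Observed failures are again kept as failures. This gives up the ITT imputation. Power is 81%, 75% or 79% with 82, 87 or 92 evaluated, because the exact test moves in steps.

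**Either way,** say whether the site-heterogeneity z-test of 10.5 and 10.7.3 still replaces the deciding test and, if so, how it is combined over the ten imputations.

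**Cost.** N stays 97. The change is wording, plus a restated power figure under the preferred option. The revision history records that Section 10 was earlier revised at FDA's request, so the sponsor may need to clear the change with the agency.

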10.3 GENERAL NOTES

Analyses of MAEs and other adverse events will be conducted at exact time points. Early events are defined as those occurring from the date of the procedure to 30 calendar days post-operatively. Late events are defined as those occurring from after 30 calendar days post-operatively (from day 31 forward). Events within six months and one year, respectively, are those occurring up to and including 183 days and 365 days following the procedure.

For categorical variables, summary statistics will include counts and proportions. Confidence limits for proportions will generally be given; for binary variables the confidence limits will be computed

¹⁴Little R and Rubin D. *Statistical Analysis with Missing Data*. 2002. John Wiley and Sons, New York.

¹⁵Steele R and Torrie J. *Principles and Procedures of Statistics*. 1960. McGraw-Hill, New York.

using the exact binomial distribution. Supportive multivariate analyses of stratified comparisons of categorical variables will be performed using appropriate logistic or Cox regression.

For continuous variables, summary statistics will include means, standard deviations, medians, and range. Groups will be compared using *t*-tests or analysis of variance, or Kruskal-Wallis tests will be used to compare more than two groups (such as trial sites). When multiple comparisons are performed after ANOVA, Scheffé's method will be used. The exact Wilcoxon test will be used to compare continuous variables where severe departures from normality are observed.

For ordinal variables, comparisons will be performed using the exact Wilcoxon rank-sum test. Unless otherwise specified, the exact form of each algorithm will be the default of SAS[®] Version 9.1 or later. Some preliminary descriptive analyses may be done with other software tools to be specified.

10.4 BASELINE COMPARABILITY ANALYSIS

A set of important demographic or prognostic variables will be compared across trial sites to determine homogeneity of trial sites in terms of baseline patient characteristics. Factors found to differ significantly by trial site will identify that variable or trial site as a possible covariate in subsequent analyses.

In the analysis of comparability of trial sites, it is anticipated that a small number of sites may have a patient enrollment that is too small to allow meaningful statistical analysis. To allow the inclusion of sites with this condition, small sites will be combined into one pseudo-site the size of which will not exceed the size of the largest trial site. It is not possible to determine the number of patients below which this aggregation will occur until after enrollment is completed, but generally trial sites with four or fewer patients may be combined.

10.5 POOLING

Data pooling incorporates two factors: combination of data across trial sites and the actual method of obtaining an estimate of the endpoint from combined data. Data will be combined from multiple trial sites for the trial analyses. The justification for this pooling is made on a clinical basis with three critical factors: The basis for pooling comes from: 1) The trial sites must implement one common protocol; 2) The sponsor must provide very close monitoring of study site compliance; and, 3) the trial sites must use common data collection procedures.¹⁶

In order to determine if there is a similar response across the sites to allow the responses to be pooled in the trial the primary safety and effectiveness proportions will be tested for homogeneity by logistic regression using a univariate model of study site within the test group. If the P-value for study site is less than 0.15, differences in study site proportions in response will be assumed to exist and the overall estimate of the proportion in the test patients will be obtained by taking a weighted average of the proportions at each site with the weight being the inverse of the variance of the proportion at that

¹⁶Meinert C. Clinical Trials: Design, Conduct, and Analysis. 1986; Oxford University Press. New York, NY

site.¹⁷ The sum of these weighted proportions divided by the sum of the weights will be the overall estimate for the study. For the safety variable, the differences of the weighted proportions will form the basis of the statistical test and for the effectiveness variable, the overall weighted proportions will be the basis of the test. The test of significance in these circumstances are fully described below.

If the heterogeneity P-value is greater than 0.15, an analysis of the primary effectiveness endpoint by the Fleiss (1993) method will be done.

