10.7 PRIMARY EFFECTIVENESS ANALYSIS

10.7.1 Primary Effectiveness Hypothesis

The primary effectiveness research hypothesis is that the treatment success rate at one year exceeds a performance goal of 80%. The null and alternative hypothesis is presented below.

$$H_0: P \leq 0.80 \quad \text{vs.} \quad H_a: P > 0.80$$

Where P is the rate of Treatment Success as defined in §10.7.2.

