10.7.2 Sample Size

The primary trial effectiveness variable is the Treatment Success rate at one year post-operatively. Treatment Success is a composite of clinically-relevant outcomes, including procedural technical success and absence of: aneurysm rupture, conversion to open repair, Type I endoleak after 30 days; Type III endoleak; clinically significant migration; aneurysm enlargement; or secondary intervention for resolution of endoleak, limb occlusion, migration, aneurysm sac expansion and/or a device defect.

The sample size is obtained by using the exact binomial distribution using PASS 2008. A sample size of 82 patients at one year in the test group will have 80.58% power against a null performance goal of 80% if the proportion of Treatment Success is 90% or higher for alpha = a one-sided 0.05. It is estimated that the rate of Treatment Success will be greater than 90%.

It is anticipated that the drop-out rate of the trial will be 15% or less. Because the larger of the two sample sizes after adjustment for loss to withdrawal is the one for effectiveness, $82/0.85 = 97$ patients will need to be recruited for this trial.

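### When sites differ, the effectiveness test switches to site weights that rise with the observed success rate, so its 5% type I error is not assured; the inflation runs from none to large.

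*Combined protocol and SAP*

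**What the plan says.** Section 10.7.1 states the hypothesis that "the treatment success rate at one year exceeds a performance goal of 80" percent, and 10.7.3 defines the tested quantity as the proportion of treated patients who meet Treatment Success. The default test is the exact binomial. Section 10.7.2 sizes the trial on that test: "A sample size of 82 patients at one year in the test group" "will have 80.58% power against a null performance goal of 80" percent "if the proportion of Treatment Success is 90% or higher for alpha = a one-sided 0.05".

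Section 10.5 adds a gate. If study site has P < 0.15 in a univariate logistic model, the overall estimate comes from "taking a weighted average of the proportions at each site with the weight being the inverse of the variance of the proportion at that" site, and for effectiveness this weighted proportion is the basis of the test. Section 10.7.3 carries this out: if sites are not homogeneous, "the method of Fleiss described above will be used in the Test arm only to obtain a weighted estimate of the proportion successful". The statistic is z = (weighted p − 0.80)/SE, with SE = (ΣW)^(−1/2).

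Three pieces of text do not fit this reading:
- 10.7.3 prints W_k as the variance, p_k(1 − p_k)/n_k. Section 10.5 describes its inverse, the stratified safety formula in 10.6.4 prints the inverse, and the SE formula makes sense only with the inverse.
- 10.7.3 rejects when z < 1.645, although the alternative is a rate above 0.80.
- The last sentence of 10.5 assigns the Fleiss method when the heterogeneity P-value is greater than 0.15.

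The synopsis gives the exact binomial test with no switch. No section says what to do with a site at 100% success, where the inverse variance is undefined.

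**The concern.** The weight n_k/[p_k(1 − p_k)] uses the observed site rate. Above 50%, p(1 − p) falls as p rises, so a site that looks better counts for more, whether it is truly better or only lucky. At equal size, a site at 94% outweighs one at 70% by (0.70 × 0.30)/(0.94 × 0.06) = 0.2100/0.0564 = 3.7 times. The weighted mean then sits above the success proportion of the treated patients.

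The SE adds to this. The branch is entered because sites appear to differ, yet the SE contains only within-site binomial variance.

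At stake is the confirmatory effectiveness claim: a site P-value, which can be small by chance, can turn a clear failure into a pass.

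**Working it through.** **1. The plan's own figure.** For n = 82 and p0 = 0.80, P(X ≥ 72) = 0.0458 and P(X ≥ 71) = 0.0836, so the exact test passes at 72 or more. Power at 0.90 is P(X ≥ 72) = 0.8057, against 80.58% stated. 82/0.85 = 96.5, rounded up to 97. Both figures reproduce, and both assume the exact test without the switch.

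**2. Where the weighted mean points.** Take equal-sized sites, half at a true 90% and half at a true 70%. The patient proportion is 80%. The large-sample weights are proportional to 1/0.09 = 11.11 and 1/0.21 = 4.76, so the weighted mean tends to (11.11 × 0.90 + 4.76 × 0.70)/15.87 = 0.84.

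**3. Worked example, all weights finite** (illustrative data, W = n/[p(1 − p)]).

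| Site result | p | W |
|---|---|---|
| 13/14 (three sites) | 0.929 | 211.08 each |
| 9/14 | 0.643 | 60.98 |
| 9/13 | 0.692 | 61.03 |
| 8/13 | 0.615 | 54.93 |

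- Crude rate: 65/82 = 79.3%; exact P(X ≥ 65 given 0.80) = 0.63.
- Likelihood-ratio P for site = 0.063, below 0.15, so the switch applies.
- ΣW = 810.16 and ΣWp = 703.25, so the weighted estimate is 0.868.
- SE = 810.16^(−1/2) = 0.0351; z = (0.868 − 0.80)/0.0351 = 1.94, above 1.645: a pass.
- The three best sites hold 42/82 = 51% of the patients and 633.23/810.16 = 78% of the weight.

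**4. Pass rate of the whole gate-then-switch procedure at a true 80%.** From the documents: gate 0.15, cut-off 1.645, N of 82 or 97, up to 25 sites, and no site above 20% of Trial Phase enrollment (at most 19 of 97; five sites give 95, so at least six are needed). Assumed: near-equal site sizes, a likelihood-ratio gate, rejection at z > 1.645, true site rates from all equal to half 90% and half 70%, and three possible rules for 100% sites. 100,000 trials were simulated per scenario.

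| Rule for 100% sites | Six sites, N = 97 | Six sites, N = 82 | Eight or more sites |
|---|---|---|---|
| Trial reverts to exact test | 6.6-15.9% | 5.7-7.4% | about 3-5% |
| Site dropped | 7.7-21.7% | 6.0-8.5% | about 1.5-5% |

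The third rule adds half a success and half a failure to such a site. It gives about 17-58% for 6 to 12 sites, 11-34% for 16 sites and 4-5% for 25 sites. The exact test alone gives 3-5% in these layouts.

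The missing rule matters. With all sites truly at 80% and N = 82, between 75% and 100% of the trials that trigger the gate contain a 100% site, across layouts of 6 to 16 sites.

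**The case against.** The strongest objection is that the procedure tested here is one reading of conflicting text. Under W_k as printed in 10.7.3, the favouring reverses: the example gives a weighted 71.0% and z = −0.02. With the printed z < 1.645, that would count as a pass for an unrelated reason. This objection stands as a limit. The inverse reading still has the better support (10.5, the stratified formula in 10.6.4 and the SE), and correcting 10.7.3 to match 10.5 would put this bias into effect.

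Second, size. A reader might infer that a device at a true 80% will generally pass far more often than 5%. The documents do not support that. Six sites is the fewest the cap allows, and up to 25 are planned. With six equal-rate sites and N = 97, the gate fires with all weights finite in only about 8% of trials; about 37% of those pass, which adds roughly 3 percentage points. With eight or more sites, dropping 100% sites or reverting to the exact test removes the excess. The largest rates need a half-count rule that the plan does not contain.

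Third, the exact test is not immune. If sites are viewed as random draws with SD 0.10 around 80%, it passes in 6.7-10.5% of trials (N = 82, 6 to 16 sites). That is fair, but the switch does not remedy it.

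That the Fleiss weighting is a recognised method does not answer the point: here it is applied to one-arm proportions near 1 with few patients per site.

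**Conclusion.** The concern holds on the inverse-variance reading with rejection at z > 1.645. The branch is biased upward, omits between-site variance, and can declare success when the crude rate is below the goal, with every weight finite. Type I error is therefore not assured at 0.05.

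How far it exceeds 0.05 cannot be fixed from the documents. It ranges from no excess (many small sites, or a conservative rule for 100% sites) to more than half of trials (few sites, wide spread, half-count rule). Site layout, true spread and the 100% rule are assumptions. Hot-deck imputation and the combination of imputed data sets were not modelled; N = 82 and N = 97 bracket the evaluable number.

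**What to change.** In 10.5 and 10.7.3, keep the exact binomial test on the pooled Trial Phase patients as the primary effectiveness test whatever the site P-value, and delete the switch to inverse-variance weighting. This agrees with the synopsis and with the stated power.

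If sites differ, report site-specific rates and, as sensitivity only, the patient-weighted proportion with a cluster-robust between-site variance. Replacing the SE with a random-effects one while keeping observed-rate weights is not enough: under the half-count rule, a DerSimonian-Laird version still passed 8-13% of equal-rate trials (6 to 16 sites) and 13-22% at 90%/70% (6 to 10 sites), N = 82.

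Reconcile the printed W_k, the direction of the z rule and the last sentence of 10.5 in the same amendment.

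The cost is wording, one extra table and the loss of the site-weighted primary estimate. Sample size and data collection do not change.
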